Developing a Patient Navigation Intervention for PrEP Continuum of Care Among Young Latino MSM  
(PrEParate)  
Study Protocol and Statistical Analysis Plan  
NCT04048382  
August 2, 2019

Using a randomized controlled trial design, a pilot test of the PN intervention will be conducted in collaboration with the Family Health Centers of San Diego (FHCS), a federally qualified health center. Bilingual research assistants will recruit 60 young adult Latino MSM at-risk for HIV in San Diego County, California; this sample size is well within the bounds of recommendations for pilot trials. After a research assistant obtains informed consent, participants will complete baseline surveys, and then the research assistant will individually randomize each participant to 1 of 2 conditions: usual care plus written information (UC) or PN. At 3- and 6-month follow-up, participants will be asked to complete surveys. Individuals randomized to PN will also be asked to participate in a key informant interview at 6-months. Participants' electronic health records (EHR) will be reviewed at 6-month follow-up to assess their engagement in the PrEP continuum. The study methods and PN intervention will be reviewed for feasibility and acceptability, as well as preliminary impact of the PN intervention in preparation for a future full-scale efficacy trial. In addition, the pilot test will evaluate preliminary impact on seven PrEP continuum-related primary outcomes (i.e., scheduled and attended PrEP consultation; PrEP prescription received; PrEP prescription filled; PrEP initiated; self-reported PrEP adherence; and PrEP follow-up medical appointment attended). Analyses will be performed under the intent-to-treat (ITT) principle. Participants will be compensated with a \$50 gift card to an online retailer at each of the three assessment time points (baseline, 3-month follow-up, 6-month follow-up). (See Appendices 1-3 for informed consents and WHO Trial Registration Data Set)

### **Patient and Public Involvement**

As suggested by Intervention Mapping, a Participatory Planning Group (PPG) of program stakeholders guided the design of the PN intervention. The PPG includes a consultant and HIV expert, potential program implementers, young Latino MSM, and community members who interact with or deliver services to people who may benefit from the intervention. The PPG was instrumental in helping us develop the intervention materials and recruitment approaches. This group will continue to meet on an as needed basis (with compensation for their time) and will assist with dissemination of research findings both in the community and in peer-reviewed publications and presentations.

### **Setting**

The pilot RCT will take place in San Diego County, California. In 2017, San Diego had an estimated population of 3,337,685 people, 33.9% of whom identified as Hispanic and 50.3% identified as male. Between 2012 and 2014, it was estimated that 3.9% of San Diego County's population identified as a sexual minority. Our study is being conducted in partnership with FHCS, which is San Diego's largest federally qualified health center, providing care to more than 140,834 patients in 2018. FHCS delivers comprehensive healthcare in 42 sites throughout San Diego County. Each site provides a wide range of health care services to sexual and gender minority patients. Although we are partnering with FHCS on this study, participants are recruited throughout San Diego County and obtain health care in various health systems, centers, and practices in the community.

### **Inclusion/Exclusion Criteria**

The following criteria are required for study inclusion: 1) age 18 to 29 years; 2) identifies as male; 3) identifies as gay/bisexual or reports having sex with men in past 12 months; 4) identifies as Latino/Hispanic; 5) self-reports being HIV-uninfected; 6) resides in San Diego County, California; 7) speaks English or Spanish; 8) is willing and able to provide informed consent; and 9) reports at least one HIV risk factor as informed by Centers for Disease Control and Prevention (CDC) guidelines. MSM are at elevated risk for HIV if they report one of the following: 1) an HIV-positive sexual partner; 2) diagnosis of a bacterial sexually transmitted infection (STI) within the past 12 months; 3) engaging in

condomless anal sex with a non-monogamous partner in the past 12 months; 4) engaging in commercial sex work in the past 12 months; 5) injection of illicit drugs and sharing of injection equipment in the past 12 months; or 6) engaging in drug treatment for injection drug use in the past 12 months. Individuals will be excluded if they self-report being HIV-positive. The intervention is designed to meet the needs of MSM who self-report their gender identity as male, but other gender identities are allowed in the study. If a potential participant indicates that their gender identity is not “male” (e.g., transgender, non-binary, gender fluid), then the participant will be informed that the study was designed for cis-male MSM; and will then be invited to determine whether they feel that they will benefit from the study based on their gender identity. Participants who previously were prescribed or are currently taking PrEP will be included in the study. Participants are not required to seek care at FHCSO to be included in the study.

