**Table 1: Description and Timing of Surveys and Health Record Data Collection**

Construct	Description of Measure	Source	BL	3 m	6 m	6m EHR
PrEP Knowledge	16-item self-report measure of knowledge related to PrEP, including use and effectiveness. Data are collected using a Likert scale.	Team developed	X	X	X	
PrEP Awareness	One survey question assessing awareness of PrEP. Categorical data are collected.	Team developed	X	X	X	
PrEP Adherence	2-item self-report survey assessing ability to take PrEP over the past 7 days, and frequency (%) with which PrEP was taken over the past 7 days. Data are collected using a Likert scale.	Team developed	X	X	X	
PrEP Attitudes	10-item PrEP Stigma and Positive Attitudes Measure assessing personal opinions about PrEP and people who use PrEP; 16 additional items assessing general attitudes and beliefs about PrEP use, provider comfort and medical mistrust related to PrEP use, side-effect concerns about PrEP use, disclosure concerns and social norms related to PrEP use, and sexual risk concerns about PrEP use. Data are collected using a Likert scale.	Mustanski et al., 2018; Pulsipher et al., 2016	X	X	X	
PrEP Barriers	5 survey items related to concerns about PrEP use, efficacy, and stigma; 5 additional items assessing potential access barriers to obtaining PrEP, including lack of health insurance coverage, difficulty finding a provider, and cost of PrEP. Data are collected using a Likert scale.	Golub et al., 2012; Pulsipher et al., 2016	X	X	X	
PrEP Efficacy Beliefs	2-item measure of beliefs regarding the efficacy of PrEP. Data are collected using a Likert scale.	Pulsipher et al., 2016	X	X	X	
Medication Self-Efficacy	4 items assessing self-efficacy to adhere to PrEP; adapted for PrEP use from the Self-Efficacy for Appropriate Medication Use Scale (SEAMS). Data are collected using a Likert scale.	Adapted from Risser, Jacobson, & Kripalani, 2007	X	X	X	
Beliefs about Medicines	Items from the Beliefs about Medicines Questionnaire (BMQ), including the BMQ-Specific subscale, a 10-item scale assessing representations of medications, and the BMC-General subscale, an 8-item subscale assessing beliefs about medicines. Data are collected using a Likert scale.	Horne, Weinman, & Hankins, 1999	X	X	X	

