Sexual Behaviors	3 items measuring over the past 3 months the total number of male anal sex partners, number of partners in which condoms were not used exclusively, and the HIV status of partners. Data are collected using numeric text entries.		X	X	X	
Mental health	21 item Depression, Anxiety, Stress Scale (DASS-21) measuring depression, anxiety, and stress over the past week. Data are collected using a Likert scale.	Lovibond & Lovibond, 1995	X	X	X	
Substance use	15 items measuring drug, alcohol, and tobacco use over the past month. Data are collected using a Likert scale.	Team developed	X	X	X	
Social support	8-item PROMIS Informational and 7-item Emotional Support Scales, respectively, measuring perceived sources of support over the past month. Data are collected using a Likert scale.	Hahn et al., 2014	X	X	X	
Patient Satisfaction with PrEP-related services	8-item Client Satisfaction Questionnaire (CSQ-8) measuring of satisfaction with PrEP-related health care services received. Data are collected using a Likert scale.	Attkisson & Greenfield, 2004		X	X	
Satisfaction with Interpersonal	For participants randomized to PN intervention only; 9-item measure of satisfaction with care provided by a patient navigator. Data are collected using a Likert scale.	Jean-Pierre et al., 2012		X	X	

Relationship with Navigator						
PN Intervention Acceptability	For participants randomized to PN, brief telephone key informant interview assessing acceptability of the PN intervention. Data are qualitative.	Team developed			X	
PrEP Initiation	Up to 10 survey items assessing whether patient had received a prescription for PrEP, decided to fill a PrEP prescription, and taken at least one dose of PrEP since the start of the study. Categorical data are collected.	Team developed	X	X	X	
Demographic Characteristics	Demographic items (e.g., age, race, gender, sexual orientation, relationship status, country of origin, U.S. citizen status, primary language, education level, employment status, income, health insurance status) have categorical response options. Age data are collected with numeric text entry.		X			
Medical Characteristics	Comorbid medical conditions, medications prescribed, history of STI testing					X

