PrEP-Related Health Care Received	Date(s) appointment scheduled for PrEP consultation; Date attended appointment for PrEP consultation; Date(s) health care provider wrote PrEP prescription(s); Date the first follow-up PrEP appointment(s) scheduled; Date(s) of follow-up medical appointment attended; Data recorded in EHR regarding adherence and discontinuation; other data regarding PrEP-related health care	Team developed				X

Abbreviations: BL = baseline; 3m = 3 month follow/up appointment; 6m = 6 month follow-up appointment; EHR = electronic health record; STI= sexually transmitted infection; PN = patient navigation

**MEMS Device Data Collection.** At baseline and 3-month follow-up, all participants will be asked if they have obtained a prescription for PrEP. Those who indicate that they have been prescribed PrEP and have taken at least one pill will be asked to track their PrEP adherence via a Medication Event Monitoring System (MEMS) device. A MEMS device is a standard prescription bottle that includes a larger lid containing a MEMS monitoring cap. During the baseline or at a 3-month follow-up visit, the research coordinator will give participants a MEMS device with instructions for its use. Participants will be instructed to place all PrEP pills into a MEMS container so when a pill is removed, the device will record date and time of removal of the medication dose using a small microcircuit. A medication “event” is removal of bottle closure, followed by replacement of closure. A study staff member will collect MEMS devices from participants in-person at the 3- and/or 6- month follow-up and connect them to a MEMS® Reader, which transfers data to a secured server via a secured web platform. Timing adherence will be calculated as percentage of time each participant took PrEP as prescribed by determining number of doses of PrEP taken at 24-hour intervals for a once daily PrEP regimen and dividing it by number of days adherence was monitored with MEMS.

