**Medical Record Data Collection.** We will collect the following data from electronic health records (EHRs) 6 months following study enrollment after obtaining a written release of information: 1) date(s) initial appointment to speak to a health care provider regarding PrEP was scheduled; 2) date participant attended an initial appointment to discuss PrEP; 3) dates and number of prescriptions written for PrEP by a health care provider; 4) date the first follow-up visit related to PrEP was scheduled; and 5) dates the participant attended follow-up appointments related to PrEP. We will document EHR data regarding PrEP initiation and adherence, barriers to PrEP adherence, exams and laboratory tests required to obtain an initial or follow-up PrEP

prescription, side effects attributed to PrEP, diagnosis and treatment of illness during the study, prescription medications, comorbid health conditions, and history of STI testing. We will also note whether the EHR indicates that participants decided to cease taking PrEP and the date of discontinuation.

**PN Intervention Encounter Data.** Using an approach developed by the Patient Navigation Research Program (PNRP), patient navigators will record process data related to the PN services provided, including: 1) number of encounters; 2) length of time of each encounter; 3) barriers experienced by patients; and 4) actions taken to reduce barriers. The patient navigators will also be asked to keep detailed qualitative notes regarding telephone, text, and in-person encounters with participants, including participants' progress in the PrEP continuum, successes in implementing the PN intervention, and challenges in implementing the PN intervention.

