## Statistical Analysis Plan

**Qualitative data.** Qualitative data (key informant interviews, navigator qualitative notes, supervisor notes) will be saved in a text file to import into NVivo for analysis. The study PIs will review the qualitative data using a content analysis technique, which identifies emergent themes occurring during discussion. Code mapping will be used to develop a preliminary set of codes (themes) corresponding to each potential strength of the PN intervention as well as every potential aspect for improvement. Then, the co-PIs will independently code the remaining data and meet to discuss and achieve consensus in coding. Once coded, the data will be summarized by theme. These data will be used to modify the PN intervention, if necessary, or will provide further indication that the PN intervention should be tested in a larger scale study.

**Quantitative data.** All quantitative data will be summarized descriptively to determine aspects of the PN intervention that worked well and potential areas of improvement of the PN intervention. Our biostatistician will be blinded to intervention assignment for participants and will conduct statistical analyses using SAS 9.4. Univariate statistics will be conducted for outcomes measured at baseline and 6-month follow-up to describe sample characteristics between the two groups (UC versus PN). Attrition in the two groups will be compared. Characteristics of individuals with missing values and individuals with no missing values will be studied. Multiple imputation technique will be implemented and sensitivity analysis will be conducted to assess if missing data is at random. Assumptions of statistical tests will be evaluated. For assessing preliminary impact, the primary outcomes are seven behaviors associated with the PrEP care continuum (i.e., appointment scheduled for PrEP consultation; appointment attended for PrEP consultation; PrEP prescription received; PrEP prescription filled; PrEP initiated; self-reported PrEP adherence over the past seven days; and PrEP follow-up medical appointment attended).

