To test the preliminary impact of the intervention, a series of logistic regression models will be conducted, with each of the 6 binary PrEP continuum primary outcome variables set as a criterion: 1) appointment scheduled for PrEP consultation; 2) appointment attended for PrEP consultation; 3) PrEP prescription received; 4) PrEP prescription filled; 5) PrEP initiated; and 6) PrEP follow-up medical appointment attended. In addition, we hypothesize that receipt of the PN intervention will be associated with increased self-reported PrEP adherence over the past seven days (also a primary outcome variable). To test the preliminary impact on the two measures of self-reported PrEP adherence, we will conduct two linear regression analyses with intervention group assignment entered as the independent variable and each measure of PrEP adherence entered as the dependent variable. Potential demographic variables (e.g., age) will be assessed for inclusion in the models as well. Finally, linear mixed models will be conducted to examine changes in 1) barriers to PrEP-related care; 2) PrEP knowledge, 3) PrEP efficacy beliefs; 4) medication beliefs, 5) PrEP attitudes; and 6) medication self-efficacy. Linear mixed models allow us to account for the dependence of the repeated measures. Different covariance structures will be implemented and the information criterion such as AIC or BIC will be used for model selection. We hypothesize that participants randomized to PN will have greater engagement in PrEP continuum behaviors compared to participants randomized to UC. Since data analyses are exploratory, and there is not adequate statistical power to evaluate efficacy of the PN intervention, these tests can only provide information regarding data trends and effect sizes. If the study and PN intervention methods are found to be feasible and acceptable, a larger study with adequate statistical power will be conducted to appropriately evaluate the efficacy of the PN intervention.

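### Current PrEP users are eligible and score as PrEP initiated in either arm by continuing, so the effect size for starting PrEP is diluted by their share

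*Combined protocol and SAP*

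**What the plan says.** All references are to the combined protocol and SAP.

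- **Inclusion/Exclusion Criteria:** "Participants who previously were prescribed or are currently taking PrEP will be included in the study". No cap on their number is stated.
- **Table 1, PrEP Initiation row:** the survey items ask, among other things, whether the person has "taken at least one dose of PrEP since the start of the study". The row is marked for baseline, 3 months and 6 months.
- **Medical Record Data Collection:** "We will document EHR data regarding PrEP initiation and adherence". No rule says how the record and the survey combine into one outcome.
- **Table 1, PrEP Adherence row:** an item on "frequency (%) with which PrEP was taken over the past 7 days" is also collected at baseline. The Randomization section places allocation straight after the baseline survey.
- **MEMS Device Data Collection:** at baseline and 3 months, devices go to "Those who indicate that they have been prescribed PrEP and have taken at least one pill". PrEP-experienced people are thus expected at entry, but this question does not separate current from past users.
- **Statistical Analysis Plan:** PrEP initiation is one of six binary primary outcomes, each with its own logistic regression. On covariates: "Potential demographic variables (e.g., age) will be assessed for inclusion in the models as well". On baseline description: "Univariate statistics will be conducted for outcomes measured at baseline and 6-month follow-up to describe sample characteristics between the two groups". On purpose: "these tests can only provide information regarding data trends and effect sizes".

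Nowhere is the initiation outcome defined for a person on PrEP at entry. The Randomization section states blocks of four and no stratification by PrEP use.

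**The concern.** A person taking PrEP at enrolment cannot start it, yet meets the only stated wording for initiation by continuing. Navigation cannot change that score, because it is met in both arms. Under the stated intention-to-treat principle these people stay in both denominators, and they pull the two arms' rates together.

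What is at stake is the meaning of one effect size. The SAP says its tests are there to give trends and effect sizes, and the opening section says preliminary impact is assessed in preparation for a full-scale efficacy trial. An initiation figure that mixes starting with continuing depends on how many users a convenience sample happens to bring in. It carries over only to a study with the same mix. The planned description of baseline outcomes by arm should show the share of users, but it does not change the model or say how they are scored.

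**Working it through.** **No figure to reproduce.** The sample size of 60 is justified only by reference to pilot-trial recommendations. The documents give no event rate, user share, alpha or power, so the inputs below are assumptions, shown as ranges.

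**Dilution.** Let q be the share of current users (equal in both arms on average under randomisation), r the proportion of users scored as initiated (the same in both arms), and p0 and p1 the initiation rates among non-users in usual care and navigation.

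- Rate in an arm = q·r + (1 − q)·p
- Risk difference (RD) = (1 − q)·(p1 − p0), whatever the value of r

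Worked case with q = 0.20, r = 1, 20% v 50%:

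- usual care 0.20 + 0.80 × 0.20 = 0.36; navigation 0.20 + 0.80 × 0.50 = 0.60
- RD = 0.24 instead of 0.30
- OR = (0.60 × 0.64)/(0.36 × 0.40) = 2.67 instead of 4.00

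| Users (q) | 20% v 50%: RD, OR | 30% v 50%: RD, OR | 10% v 30%: RD, OR |
|---|---|---|---|
| 0% | 30 points, 4.0 | 20, 2.3 | 20, 3.9 |
| 5% | 28.5, 3.5 | 19, 2.2 | 19, 3.0 |
| 10% | 27, 3.1 | 18, 2.1 | 18, 2.5 |
| 20% | 24, 2.7 | 16, 1.9 | 16, 2.0 |
| 30% | 21, 2.4 | 14, 1.8 | 14, 1.8 |

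Users need not all score as initiated. At q = 0.20 with r = 0.8, the rates are 0.32 and 0.56, so RD is again 0.24 and OR 2.7.

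**Precision at 20% users, 20% v 50%** (unpooled standard errors):

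- All 60: √[(0.36 × 0.64 + 0.60 × 0.40)/30] = 0.125; RD/SE = 0.24/0.125 = 1.92
- 48 non-users: √[(0.20 × 0.80 + 0.50 × 0.50)/24] = 0.131; RD/SE = 0.30/0.131 = 2.30

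At 30% v 50% the two ratios are 1.26 and 1.44. The gain is specific to initiation. For an outcome where users respond as non-users do, leaving them out loses information: 0.30/0.117 = 2.57 in all 60 against 2.30 in 48.

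**Covariate adjustment.** Take 5/24 v 12/24 initiated among non-users and 6/6 v 6/6 among users.

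- Unadjusted, all participants: 11/30 v 18/30, OR = (18/12)/(11/19) = 2.6.
- With baseline use added, the user coefficient diverges (SE about 13,000). The arm log OR is ln[(12/12)/(5/19)] = 1.335 (OR 3.8), with SE √(1/12 + 1/12 + 1/5 + 1/19) = 0.648. Both equal the non-user analysis.

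Adjustment and restriction thus agree on the arm effect when every user scores as initiated.

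**Chance imbalance.** With 12 users among 60, a split at least as uneven as 8 v 4 occurs about 33% of the time (hypergeometric, ignoring the blocks of four). At 20% v 50%, with 8 users in usual care and 4 in navigation, the expected rates are (8 + 22 × 0.20)/30 = 0.413 and (4 + 26 × 0.50)/30 = 0.567, so RD is 0.153. With the split reversed they are (4 + 26 × 0.20)/30 = 0.307 and (8 + 22 × 0.50)/30 = 0.633, so RD is 0.327. The all-participant figure can therefore err in either direction in a single trial. The non-user estimate does not move with the split in this way.

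**Hypothetical later trial.** Suppose it took initiation as its endpoint, enrolled the same mix with 20% users, and had rates of 20% v 50% (pooled-variance formula, two-sided 5%, 80% power). It would need about 67 per arm on the all-participant outcome. Analysed in non-users it would need 39 per arm, or 39/0.80 ≈ 49 per arm enrolled. The documents state none of these conditions.

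**The case against.** The strongest reply is that the plan limits the consequence itself. The analyses are exploratory and admittedly underpowered, and a larger study follows only if methods prove feasible and acceptable. The all-randomised comparison is what the plan commits to, and it is valid for the people enrolled. The trial chooses to include users, and one of its educational modules concerns adherence. The planned baseline description should reveal the share of users, and at 5% users a 30-point difference becomes only 28.5. All of this stands, and it limits the weight of the point. It does not remove it, because the effect size is what the SAP says these tests provide, and description after the fact supplies no scoring rule.

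Four stronger readings are tempting and are not supported:

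- **That the intention-to-treat result is biased or should give way to the non-user analysis.** It is an unbiased contrast for the enrolled mix, and the opening section adopts the principle. The non-user estimate answers a different question and belongs beside it.
- **That baseline use cannot be a covariate because the logistic model may separate.** Only the user coefficient diverges. The arm estimate and its SE equal those of the restricted analysis.
- **That the larger study will be mis-sized by the numbers shown.** No passage states its endpoint, eligibility or mix.
- **That every outcome on the continuum is diluted in the same way.** Current users may still respond to navigation on consultation and prescription outcomes. There the documents show only that the scoring of users is unstated.

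**Conclusion.** The point holds for the PrEP-initiated outcome and should be fixed. Under the only wording given, continuing users score as initiated in either arm, and the planned model neither separates them nor adjusts for them. As an effect size for starting PrEP, the expected risk difference shrinks by the factor (1 − share of users), and the odds ratio moves towards 1. The direction is certain if any users enrol and the wording is applied as written.

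The size is not known. It rests on an assumed user share and assumed event rates, and on users scoring alike in both arms. Over 5% to 30% users, at 20% v 50%, the odds ratio falls from 4.0 to between 3.5 and 2.4. Neither the validity of the intention-to-treat comparison nor the decision to progress is in question.

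**What to change.** 1. **Define the outcome.** State that PrEP initiated means starting or restarting after randomisation, and how survey and health-record data combine. Identify current users from the pre-randomisation survey, using the 7-day PrEP use item together with the initiation items also asked at baseline. The 7-day item alone would miss someone who lapsed shortly before enrolment. The baseline form of the initiation items needs checking, since dosing counted from study start means little on the day of entry. Past users not taking PrEP at baseline stay among those who can start.
2. **Report two initiation estimates.** Keep the all-randomised intention-to-treat result. Pre-specify beside it the as-randomised estimate among participants not on PrEP at baseline, as the figure to carry forward for starting PrEP. Give the share of users by arm. Adjusting for baseline use is an acceptable route to the same arm estimate when all users score as initiated. Name Firth's penalised logistic regression if the fit separates; being penalised, its estimate will differ somewhat from the unpenalised one.
3. **Pre-specify baseline PrEP use as a covariate** for self-reported adherence and for follow-up visit attended, in all randomised participants, with Firth as the fallback for the visit outcome. If users attend with an assumed probability of 0.8 or 0.9, the chance that all attend is 26% or 53% with 6 users (0.8⁶, 0.9⁶), and 7% or 28% with 12.

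**Cost.** SAP wording only; no new data and no change to eligibility. The non-user estimate rests on fewer people: about 48 of 60 at 20% users, with an SE of about 13.1 against 12.5 points at 20% v 50%.
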